### 11.2 Study Day

Day 1 is defined as the date of first study drug administration. For subjects who used any study drug but did not have a recorded date of first study drug administration (e.g., due to missing Week 4 visit), Day 1 is defined as randomization date + 1. Study day is calculated relative to the date of Day 1.

### 11.3 Baseline and Change from Baseline

Baseline value is defined as the last non-missing value prior to the first dose of study drug. Change from baseline is defined as the post-baseline value minus the baseline value unless otherwise specified. Percent change from baseline is calculated as follows: Percent change = (Change from baseline / Baseline) \* 100.

### 11.4 Analysis Visit Window

Efficacy and safety endpoints will be analyzed according to their windowed visits defined by actual study day. If more than one visit occurs within a single visit window, then the analysis will take the one closest to the target day. If the 2 visits are equidistant from the target day, the later visit will be used. A later visit within the window will be used for LOCF.

The following analysis visit windows will apply:

Visit	Week	Target Day	Efficacy Assessment Window	Safety Assessment Window
2	Baseline	0	On or prior to date of first dose	On or prior to date of first dose
3	4	28	Post-dose – Day 42	Post-dose – Day 42
4	8	56	Day 43 – Day 70	Day 43 – Day 70
5	12	84	Day 71 – Day 98	Day 71 – Day 98
6	16	112	Day 99 – Day 126	Day 99 – Day 126
7	20	140	Day 127 – Day 154	Day 127 – Day 154
8	24	168	≥Day 155	≥Day 155
9 (Follow-Up)	25	LD+7	> LD+15	> LD+15

LD = Last dose date

Visits 3 through 8 are on-treatment visits. Therefore, only on-drug assessments or assessments performed within 15 days post last dose are to be analyzed within those windows, according to their actual study day. Visit 9 is an off-treatment visit, which will be analyzed according to their number of days after last dose, regardless of the actual study day. For example, a subject who has Visit 4 on Day 56, then discontinues with last dose on Day 84 and returns for Early Termination on Day 100 will have no data within the Visit 6 window. The Early Termination visit must be analyzed as Visit 9. For this subject, data for Visits 5, 6, 7, and 8 would be carried forward from Visit 4 in an LOCF analysis. If the last dose date is unknown, then all visits will be analyzed as on-treatment based on actual study day (i.e., no Visit 9 will be identified for the subject).

Subjects who permanently discontinue the study drug for any reason or who withdraw from the study prematurely prior to the end of the Double-Blind Treatment Period should undergo the ETV followed by the EOS Safety Follow-up Period Visit. In the event that the ETV or Week 24 Visit occurs > 1 week following the last dose of the study drug, the EOS Safety Follow-up Visit may not be required. If necessary, the Investigator may decide to extend the EOS Safety Follow-up Visits beyond 1 week to monitor recovery of safety parameters (eg, lymphopenia).

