7.2.4 Early Termination Visit

- Review any concomitant medication changes since the previous study visit
- Assess IP compliance/accountability
- Perform a partial physical examination with focus on previously noted abnormalities in organ systems, including skin
- Measure weight
- Measure waist circumference
- Measure vital signs (systolic and diastolic blood pressure, heart rate, and respiratory rate) with subject in a seated position
- Record a 12-lead ECG
- Perform a UPT for females of childbearing potential. Ensure that female subjects of childbearing potential are using approved method(s) of contraception.
- Obtain blood and urine samples for routine laboratory profile evaluations including hematology, clinical chemistry, and urinalysis
- Blood collection for lymphocyte subset & Ab titer study
- Record any AEs
- Perform psoriasis assessments:
 - PASI, BSA, IGA
 - NAPSI for target fingernail, PSSI, PP PGA (if applicable)
- Have the subject perform the following assessments:
 - Pruritus NRS

- DLQI, SF-12, QIDS-SR16, WPAI: PSO, HEOR

7.2.5 Safety Follow-up Visit (Week 25 [+3 days], or 1 Week [+3 days] after ETV, unless final dose was taken >7 days prior to Week 24/ETV)

- Review any concomitant medications used since the previous study visit
- Perform a partial physical examination with focus on previously noted abnormalities in organ systems, including skin
- Measure vital signs (systolic and diastolic blood pressure, heart rate, and respiratory rate) with subject in a seated position
- Record a 12-lead ECG
- Perform a UPT for females of childbearing potential. Ensure that female subjects of childbearing potential are using approved method(s) of contraception.
- Record any AEs
- Perform psoriasis assessments:
 - PASI, BSA, IGA
 - NAPSI for the target fingernail , PSSI, PP PGA (if applicable)
- Have the subject perform the following assessments:
 - Pruritus NRS
 - DLQI, SF-12, QIDS-SR16, WPAI: PSO, HEOR

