MI for missing IGA scores : The imputation of post-baseline IGA scores will be performed following a similar approach as described for PASI scores. Intermittent missing IGA scores will be imputed separately for each treatment group using the Markov Chain Monte Carlo (MCMC) method where 50 copies of the dataset with monotonic missing pattern will be generated. For each of the 50 datasets, missing values at scheduled visits (Weeks 4, 8, 12, 16, 20 and 24) will be imputed using a logistic regression model including baseline BMI, baseline IGA score, and IGA scores at the previous scheduled visits. SAS Proc MI using the logistic regression method for monotone data will be used for the imputation. IGA Treatment Success status (Yes/No) will then be derived for each imputed dataset.

The imputation of missing post-baseline BSA, NAPSI, and NRS scores will be performed using a similar method as described for PASI. The imputation of missing post-baseline PSSI and PP PGA scores will be performed using a similar method as described for IGA. No imputation will be done to the health-related quality of life endpoints or safety endpoints and only observed values will be analyzed.

mNRI: Subjects who used rescue medications or discontinued due to unsatisfactory therapeutic effect are considered as treatment failures (i.e., non-responder) for all time points after the initiation of rescue medications or subject discontinuation. Other missing data are not to be imputed and are to be kept as missing.

LOCF: The last observed value will be carried forward for any subsequent missing values. Baseline values will not be carried forward.

All QoL endpoints will be analyzed using the OC approach. No other imputations will be made unless otherwise specified.

Note that Early Termination visit data will be analyzed at the closest visit where data are not obtained. Full details will be provided in the SAP.

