The imputation of missing post-baseline BSA, PSSI final score, NAPSI, and NRS scores will be performed using a similar method as described for PASI. The imputation of missing post-baseline PP PGA scores will be performed using a similar method as described for IGA. A pre-specified seed number of 132138 will be used in all imputation procedures. No imputation will be done to the health-related quality of life endpoints or safety endpoints.

- **Observed cases (OC)**: No imputation will be performed, only observed values will be analyzed.
- **m-NRI (response endpoint only)**: Subjects who used rescue medications or discontinued due to unsatisfactory therapeutic effect are considered as treatment failures (i.e., non-responder) for all time points after the initiation of rescue medications or subject discontinuation. For example, if a subject discontinued due to lack of efficacy, all visits

after the last planned visits will be imputed to non-responders. If a subject used rescue medication during the study, all visits after the start of the rescue medication will be imputed to non-responders regardless if the subject had an assessment or not. Other subjects with missing data will be kept as missing (i.e., no imputation). Discontinuation due to unsatisfactory therapeutic effect will be identified by discontinuation reason = "Other" with a comment "lack of efficacy" on the eCRF.

- **LOCF:** The last observed value will be carried forward for any subsequent missing values. Baseline values will not be carried forward.

A summary of the imputation methods for all efficacy endpoints is shown below:

Endpoint	Analysis Population	Imputation Methods
PASI-75 at Week 24	FAS	MI, m-NRI, LOCF, OC
	PP	m-NRI
IGA score of clear or almost clear at Week 24	FAS	MI, m-NRI, LOCF, OC
	PP	m-NRI
Change from Baseline and percent change from Baseline in PASI Total Score by Visit	FAS	MI, LOCF, OC
	PP	OC
PASI-50 and PASI-75 by Visit	FAS	MI, m-NRI, LOCF, OC
	PP	m-NRI
IGA score of clear or almost clear by Visit	FAS	MI, m-NRI, LOCF, OC
	PP	m-NRI
Change from Baseline and percent change from Baseline in BSA by Visit	FAS	MI, LOCF, OC
	PP	OC
Change from Baseline in NPSI by Visit	FAS	MI, LOCF, OC
	PP	OC
Change from Baseline in PSSI by Visit	FAS	MI, LOCF, OC
	PP	OC
Change from Baseline in PP PGA by Visit	FAS	MI, LOCF, OC
	PP	OC
Change from Baseline in NRS by Visit	FAS	MI, LOCF, OC
	PP	OC
Time to PASI-75	FAS	OC
Time to achieving an IGA score of clear or almost clear	FAS	OC
QIDS-SR 16	FAS	OC

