### 12.7.3 Health-related Quality of Life Endpoints

The Health Outcome/Quality of Life endpoints are the change from baseline in the following health outcome/QoL assessments at Weeks 12, 16, and 24:

- Quick Inventory of Depressive Symptomatology-Self Report (16 Items) (QIDS-SR16) total score. The total score (range 0-27) is calculated as the sum of the following 9 items: Highest score on any sleep items (Q1-Q4), Q5, highest score on any appetite/weight items (Q6-Q9), Q10, Q11, Q12, Q13, Q14, highest score on either psychomotor items (Q15 & Q16). The total score will be considered as missing if any of the component score is missing.
- The Dermatology Life Quality Index (DLQI) total score (0-30) will be calculated as the sum of 10 questions with each ranging from 0 to 3. The scoring of each answer is as follows:

Very much	Scored 3
A lot	Scored 2
A little	Scored 1
Not at all	Scored 0
Not relevant	Scored 0
Question unanswered	Scored 0
Question 7: "prevented work or studying"	Scored 3

If one question is left unanswered this is scored 0 and the scores are summed and expressed as usual out of a maximum of 30. If two or more questions are left unanswered the total DLQI score is missing. If question 7a is answered 'no' or 'not relevant', then the answer of 7b will be ignored. Additionally, the score of each of 6 domains (daily activities, personal relationships, symptoms and feelings, leisure, work/school, and treatment) will be summarized separately.

- The SF-12 summary scales will be calculated using the SF-12 Health Survey Standard Scoring software. Summary scores will be computed for Physical Summary (PCS) and Mental Summary (MCS). Subscores will also be computed for the following 8 domains:
  - Physical Functioning (PF)
  - Role-Physical (RP)
  - Bodily Pain (BP)

- Social Functioning (SF)
  - Mental Health (MH)
  - Role-Emotional (RE)
  - Vitality (VT)
  - General Health (GH)
- Work Productivity and Activity Impairment Questionnaire: Psoriasis (WPAI:PSO) score. WPAI-PSO outcomes are expressed as impairment percentages, with higher numbers indicating greater impairment and less productivity, i.e., worse outcomes as follows
    - The percent work time missed due to psoriasis will be summarized for all subjects who answer “Yes” to Question 1, “Are you currently employed?”. This will be calculated using the following formula:  $100 * ((\text{Question 2}) / (\text{Question 2} + \text{Question 4}))$

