Change from Baseline in DLQI Total Score by Visit  
Full Analysis Set, OC

	PPC-06 400 mg QD (N=XX)	PPC-06 400 mg BID (N=XX)	PPC-06 600 mg BID (N=XX)	Placebo (N=XX)
Baseline				
N	XX	XX	XX	XX
Mean (SD)	XX.X (XX.X)	XX.X (XX.X)	XX.X (XX.X)	XX.X (XX.X)
Median	XX	XX	XX	XX
Minimum, Maximum	XX, XX	XX, XX	XX, XX	XX, XX
Week 12				
N	XX	XX	XX	XX
Mean (SD)	XX.X (XX.X)	XX.X (XX.X)	XX.X (XX.X)	XX.X (XX.X)
Median	XX	XX	XX	XX
Minimum, Maximum	XX, XX	XX, XX	XX, XX	XX, XX
Change from baseline				
N	XX	XX	XX	XX
Mean (SD)	XX.X (XX.X)	XX.X (XX.X)	XX.X (XX.X)	XX.X (XX.X)
Median	XX	XX	XX	XX
Minimum, Maximum	XX, XX	XX, XX	XX, XX	XX, XX

<Repeat for Week 16, Week 24>

Note: DLQI= Dermatology Life Quality Index. OC= Observed Cases.

Generated on XX/XX/XX:XXXX by XXXXXX / Uses: XXXX / Reference: Listings XXXX

Table 14.2.3.2.2: Analysis of Quality of Life Outcome  
Change from Baseline in DLQI Individual Domains by Visit  
Full Analysis Set, OC

	PPC-06 400 mg QD (N=XX)	PPC-06 400 mg BID (N=XX)	PPC-06 600 mg BID (N=XX)	Placebo (N=XX)
Symptoms and Feelings				
Baseline				
N	XX	XX	XX	XX
Mean (SD)	XX.X (XX.X)	XX.X (XX.X)	XX.X (XX.X)	XX.X (XX.X)
Median	XX	XX	XX	XX
Minimum, Maximum	XX, XX	XX, XX	XX, XX	XX, XX
Week 12				
N	XX	XX	XX	XX
Mean (SD)	XX.X (XX.X)	XX.X (XX.X)	XX.X (XX.X)	XX.X (XX.X)
Median	XX	XX	XX	XX
Minimum, Maximum	XX, XX	XX, XX	XX, XX	XX, XX
Change from baseline				
N	XX	XX	XX	XX
Mean (SD)	XX.X (XX.X)	XX.X (XX.X)	XX.X (XX.X)	XX.X (XX.X)
Median	XX	XX	XX	XX
Minimum, Maximum	XX, XX	XX, XX	XX, XX	XX, XX
<Repeat for Week 16, Week 24>				
<Repeat for other domains: Daily Activities, Leisure, Personal Relationships >				

Note: DLQI= Dermatology Life Quality Index. OC = Observed Cases.

Generated on XX/XX/XX:XXXX by XXXXX / Uses: XXXX / Reference: Listings XXXX

Table 14.2.3.2.2: Analysis of Quality of Life Outcome  
 Change from Baseline in DLQI Individual Domains by Visit  
 Full Analysis Set, OC

	PPC-06 400 mg QD (N=XX)	PPC-06 400 mg BID (N=XX)	PPC-06 600 mg BID (N=XX)	Placebo (N=XX)
Work and School				
Baseline, n (%)				
Yes	XX (XX.X)	XX (XX.X)	XX (XX.X)	XX (XX.X)
No	XX (XX.X)	XX (XX.X)	XX (XX.X)	XX (XX.X)
Not relevant	XX (XX.X)	XX (XX.X)	XX (XX.X)	XX (XX.X)
Week 12, n (%)				
Yes	XX (XX.X)	XX (XX.X)	XX (XX.X)	XX (XX.X)
No	XX (XX.X)	XX (XX.X)	XX (XX.X)	XX (XX.X)
Not relevant	XX (XX.X)	XX (XX.X)	XX (XX.X)	XX (XX.X)
<Repeat for Week 16, Week 24>				

Note: DLQI= Dermatology Life Quality Index. OC = Observed Cases.

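### Under SAP 11.4, quality-of-life scores from early termination visits on Days 1–70 or 127–154 have no summary row

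*SAP*

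**What the plan says.** Protocol Table 1-1 schedules the QoL instruments at baseline, Weeks 12, 16 and 24, the ETV and Week 25. Protocol 7.2.4 repeats that the ETV includes "DLQI, SF-12, QIDS-SR16, WPAI: PSO, HEOR", on whatever study day the ETV falls.

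For the analysis, SAP 11.4 says: "Efficacy and safety endpoints will be analyzed according to their windowed visits defined by actual study day". It has a single set of 4-weekly windows for all instruments. The Week 4 window is "Post-dose – Day 42". Week 8 is Days 43–70, Week 12 is Days 71–98, Week 16 is Days 99–126, Week 20 is Days 127–154, and Week 24 starts at Day 155. An assessment more than 15 days after the last dose becomes Visit 9. If two visits share a window, the one nearer the target day is used.

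QoL falls under this rule. SAP Section 9 introduces its table with "A summary of the imputation methods for all efficacy endpoints is shown below", and that table lists all five QoL instruments as FAS, observed cases. The same section rules out imputation for them.

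The QoL endpoints in SAP 12.7.3 are "the change from baseline in the following health outcome/QoL assessments at Weeks 12, 16, and 24". The table shells (14.2.3.1 to 14.2.3.5) show baseline and Week 12, followed by the instruction "Repeat for Week 16, Week 24".

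Protocol 8.7.3 has a different rule: "Note that Early Termination visit data will be analyzed at the closest visit where data are not obtained". It leaves full details to the SAP, and Protocol 8.10 gives the SAP precedence. SAP Section 13 lists only the PP PGA change.

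**The concern.** The windows fit PASI and IGA, which are measured at every 4-weekly visit. They do not fit instruments that skip Weeks 4, 8 and 20. An ETV score labelled with one of those weeks has no row to enter, and without carry-forward it cannot reach a later row.

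QoL belongs to the first secondary objective, and the plan assumes that half the subjects drop out. Scores deliberately collected from people who stop early, for example because of unresolved GI intolerability (the plan's own example of a reason for an ETV), would then be missing from the QoL tables. The summaries would lean further towards subjects who stayed on drug.

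**Working it through.** **Plan's own dropout figure.** Protocol 8.2 and SAP Section 7 assume 100 subjects per arm and 50% dropout: 100 × (1 − 0.50) = 50 completers, so 50 dropouts per arm and 200 in all. The stated power of at least 84% is consistent with this. With 50 per arm and 15% against 45%, power per endpoint is Φ[(0.30 − 1.96·√(2·0.30·0.70/50)) / √((0.15·0.85 + 0.45·0.55)/50)] = Φ[(0.300 − 0.180)/0.0866] = Φ(1.39) = 0.918. Treating the two endpoints as independent gives 0.918² = 0.842. The point below uses only the 50% dropout.

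**Days that lead to a window without a QoL row.**

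| Window | Days | Length | QoL row? |
|---|---|---|---|
| Week 4 | 1–42 | 42 | No |
| Week 8 | 43–70 | 28 | No |
| Week 12 | 71–98 | 28 | Yes |
| Week 16 | 99–126 | 28 | Yes |
| Week 20 | 127–154 | 28 | No |
| Week 24 | from 155 | – | Yes |

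42 + 28 + 28 = 98 days. Over 168 treatment days, 98/168 = 58%. Counting ETVs only up to Day 167 gives 98/167 = 59%; counting only up to Day 154 gives 98/154 = 64%.

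**Dependence on dropout timing.** The documents give no timing, so the share is shown under assumed timings, with each ETV within 15 days of the last dose. Ranges reflect the Day 154 and Day 167 cut-offs.

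| Assumed ETV timing | Share in windows without a row |
|---|---|
| All on Days 71–126 | 0% |
| Even, all after Day 70 | 29–33% |
| Linearly increasing | 46–54% |
| Uniform | 59–64% |
| Constant hazard, 50% by Day 168 | 63–67% |
| Front-loaded, half-life 84 days | 68–71% |
| Front-loaded, half-life 42 days | 78–79% |

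Another early pattern, with 70% of ETVs by Day 70 and the rest even over Days 71–168, gives 0.70 + 0.30 × 28/98 = 79%.

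**Subjects with no post-baseline QoL in any row.** A Week 20-window dropout has normally already given Week 12 and Week 16 scores, and both are tabulated. The group left with nothing is therefore those with an ETV on Days 1–70: 70/168 = 42% of dropouts under uniform timing, and 0.417 × 50 = 20.8 per arm. A follow-up visit 7 days after an ETV on Days 64–70 falls in the Week 12 window. Allowing for that leaves 63 days: 63/167 = 38% to 63/154 = 41%. The corresponding range is 14–17% for linearly increasing dropout and 69–70% for the 42-day half-life.

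**Two further routes to the listings.**
- An ETV after the target day in the Week 12 or Week 16 window is displaced by the scheduled visit. With scheduled visits on target, that is 14 + 14 = 28 days (28/167 = 17% to 28/154 = 18%). These subjects still have the scheduled score in that row.
- An ETV more than 15 days after the last dose becomes Visit 9, which has no QoL row. Protocol 4.1 and 6.3 send subjects who have been off drug for more than two weeks to an ETV, so this can happen in ordinary conduct.

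**NAPSI.** It has the same visit schedule, but SAP Section 9 analyses it on the FAS by MI, LOCF and observed cases. Under LOCF, an ETV score windowed to Week 4, 8 or 20 is carried into the later rows. Only the observed-case tables clearly lose it.

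**The case against.** The strongest reply is that this is a small reporting gap. QoL is summarised descriptively with no tests, every score is in the by-subject listings, and the co-primary analyses are untouched. All of that stands, and it limits the weight of the point.

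The reply also disposes of several stronger readings that a reader might draw:

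- *Most dropouts lose their QoL data.* This needs a dropout timing that the documents do not give, and it treats Week 20-window dropouts as having nothing when their Week 12 and 16 scores are normally tabulated. A total of 117 lost scores (0.583 × 50 × 4) would further require every dropout to attend an ETV. Both documents say that subjects who withdraw full consent or are lost to follow-up are not expected to.
- *NAPSI scores appear in no summary.* LOCF and MI are also planned.
- *The protocol says the opposite of the SAP.* The SAP windows break at the midpoints between target days (42, 70, 98, 126, 154), so they already assign to the nearest visit. What is dropped is the condition that the visit has no data. For QoL that condition is itself ambiguous, because Weeks 4, 8 and 20 never have QoL data.
- *Windowing makes Week 24 a near completers-only row.* That follows mainly from the observed-case choice, which is already in the protocol. Of the scores in windows without a row, moving each to the nearest unfilled QoL visit would bring only those from Days 127–154 to Week 24: 28/168 × 50, about 8 per arm under uniform timing.

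The reply is also right that relabelling is a poor remedy. A Day 10 score taken during titration would be shown as Week 12 (Day 84), 74 days away. HEOR asks for counts since the start of medication, so an early count would understate use.

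**Conclusion.** The gap is real and narrow. The SAP collects ETV QoL scores, windows them by study day, and provides no summary row for those on Days 1–70 or 127–154, or for those more than 15 days after the last dose. Under uniform dropout this affects about 58% of attended ETVs, with 0% to about 79% under other timings. Subjects with no post-baseline QoL in any row are about 42% of dropouts under uniform timing. That is at most about 21 per arm, fewer once withdrawn consent and loss to follow-up are removed, and more only if dropout is concentrated early.

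These figures rest on the plan's 50% dropout, an assumed timing, scheduled visits attended on target, and, for the day counts, an ETV within 15 days of the last dose. That the missing scores are worse than the tabulated ones is plausible, but the documents do not show it. The unlisted departure from Protocol 8.7.3 is a documentation gap and does not depend on any of these assumptions.

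**What to change.** 1. Add a row, *End of treatment (last on-treatment value, including ETV)*, to Tables 14.2.3.1–14.2.3.5 and to the NAPSI observed-case tables (14.2.2.6.3 and 14.2.2.6.4).
2. For HEOR, show time on treatment beside the counts in that row.
3. State how the row treats an ETV more than 15 days after the last dose. Under the present on-treatment definition it stays out, and a footnote should then give the number of such scores.
4. Record in SAP Section 13 that the Protocol 8.7.3 rule for ETV data is not followed, and why.
5. Do not relabel early ETV scores as Week 12.

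The cost is one extra row per table and a few lines of SAP text, with no new data. The drawback is that the row mixes values taken at different times on treatment, which its label should make plain.

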5.4 Discontinuation of Treatment or Assessments

Subjects can be removed from the study for any of the following reasons:

- AE(s)
- Protocol violation
- Withdrawal by subject (subject voluntarily discontinued study participation)
- Lost to follow-up
- Pregnancy
- Study terminated by sponsor
- Investigator decision
- Non-compliance with study drug (<80% or >120%)
- Loss of ability to freely provide consent through imprisonment or involuntary incarceration for treatment of either a psychiatric or physical (eg, infectious disease) illness
- Unblinding of a subject for any reason

All subjects meeting the above withdrawal criteria are to be evaluated at the safety follow-up EOS visits unless they have withdrawn full consent. The reason for a subject's permanent withdrawal is to be recorded on the appropriate electronic case report form (eCRF). Subjects

who prematurely withdraw from the study for AEs are to be monitored for up to 30 days after the subject stopped study treatment or until the abnormal parameter resolves or stabilizes.

Pregnancies are to be reported to the sponsor or designee within 24 hours of learning of its occurrence, and the pregnancy is to be monitored to determine outcome. Investigators are to document their attempts to contact subjects who are lost to follow-up.

As a class, FAEs are known to have an effect on lymphocyte and eosinophil counts and can have hepatotoxic and nephrotoxic effects at excessive exposures. The following study drug discontinuation criteria are to be implemented to reduce the risk of toxicity for individual subjects and to investigate the time course of recovery of affected safety parameters.

If any of the following criteria are met, study treatment will be permanently discontinued and the subject will be scheduled for an ETV followed by the Safety Follow-up Visit.

- Lymphocytes $<500/\text{mm}^3$ at any visit
- Lymphocytes $<800/\text{mm}^3$ on 3 consecutive visits
- ALT or AST $>8\times\text{ULN}$ on repeat examination (if assumed increase is related to study drug)
- ALT or AST $>5\times\text{ULN}$ for more than 2 weeks on repeat examination (if assumed increase is related to study drug)
- ALT or AST $>3\times\text{ULN}$ and either total bilirubin $>2 \times$ the ULN or International Normalized Ratio (INR) >1.5 on repeat examination (if assumed increase is related to study drug) in presence of normal alk phosphate.

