- ALT or AST $>3\times\text{ULN}$ with concurrent appearance or worsening of fatigue, nausea, vomiting, right upper quadrant pain or tenderness, fever, rash, or eosinophilia ($>5\%$ eosinophils on differential leukocyte count)
- Serum creatinine $>1.5\times\text{ULN}$ on repeat exam (if assumed increase is related to study drug)
- Proteinuria measured as 3+ or above in urine dipstick on 2 consecutive samples, 4 weeks apart
- If advised by the Medical Monitor or PML experts.

Laboratory tests can be repeated earlier than the next scheduled consecutive visit at the investigator's discretion and any associated safety issue should be followed up as per the Investigator's clinical judgment until resolution/stabilization.

Replacement Policy

Subjects who prematurely discontinue from the study after randomization will not be replaced.

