7.5.3 Safety Laboratory Assessments

Blood and urine samples for laboratory tests (hematology, serum biochemistry, and urinalysis) will be collected as specified in [Table 1-1](#). Clinical laboratory specimens will be analyzed by a central licensed and accredited laboratory facility according to the laboratory's standard operating procedures.

If any of the laboratory parameters of interest show a significant shift from baseline, subjects will then be scheduled for an interim visit within 2 weeks to repeat the laboratory measurements.

Non-fasting blood samples will be obtained at each visit for laboratory analysis of serum glucose, lipid panel, hsCRP, and PD study.

No blood is to be collected for the PD study at Screening.

Blood samples for serology assessment (HIV, HBsAg, Anti-HBc, and HCV) will be obtained at Visit 1 (Screening).

Lymphocyte subsets and antibody titer will be collected for safety assessments per [Table 1-1](#).

The routine clinical laboratory tests to be performed are provided in [Table 7-2](#).

The investigator may collect additional blood or urine samples to repeat any laboratory test that was abnormal post-dosing, or was within normal limits at Baseline, and is considered clinically significant. Abnormal laboratory results at the last scheduled visit may require additional collection of samples on an "as needed" basis until: a) the values return to the baseline value, b) the values are within normal limits, c) the values are clinically stable, or d) the investigator determines that further follow-up is unnecessary. The investigator will record the date and time of all additional samples collected. If the investigator establishes a clear explanation for the laboratory abnormality, he/she will record this explanation in the eCRFs.

Blood will also be collected and evaluated for PD study per [Table 1-1](#).

Table 7-2 Routine Clinical Laboratory Assessments

Hematology		
• Platelet Count	RBC Indices:	Automated WBC Differential:
• RBC Count	• MCV	• Neutrophils
• WBC Count (absolute)	• MCHC	• Lymphocytes
• Lymphocytes (absolute)	• MCH	• Monocytes
• Neutrophils (absolute)		• Eosinophils
• Monocytes (absolute)		• Basophils
• Hemoglobin		
• Hematocrit		
• Lymphocyte subset (collected and will be assessed)		
• Antibody titer (collected and stored with assessment done as required)		
Chemistry		
• Sodium	• Creatine Kinase	• Cholesterol
• Potassium	• Alkaline Phosphatase	• Triglycerides
• Chloride	• GGT	• HDL Cholesterol

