## **12.9.2 Clinical Laboratory Testing**

Clinical laboratory values will be reported as complete listings of individual subject data. All laboratory values will be classified as normal, low, or high based on normal ranges supplied by the laboratory. Subjects with values outside the normal range will be flagged and summarized using shift tables. A separate listing and table will identify and summarize subjects with markedly abnormal values. For quantitative measures, observed and changes in clinical laboratory values will be analyzed descriptively by time of collection and treatment group.

Additionally, lymphocyte counts will be summarized by clinical response of PASI-50 and PASI-75 (Yes/No) at Week 24. Lymphocyte counts and hs-CRP will also be plotted against PASI scores by visit and treatment. The correlation coefficient will be reported.

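### The one-value-per-window rule also governs safety laboratory data, so the outlined by-visit and shift tables omit most off-schedule results, and no outlined laboratory table recovers an abnormality first seen off-schedule

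*SAP*

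**What the plan says.** SAP 11.4 opens with its scope: "Efficacy and safety endpoints will be analyzed according to their windowed visits defined by actual study day". Where a window holds several visits, "If more than one visit occurs within a single visit window, then the analysis will take the one closest to the target day", and "If the 2 visits are equidistant from the target day, the later visit will be used". The safety windows are identical to the efficacy windows. From Week 4 to Week 20 each ends 14 days after its target day (Week 8, for example, has target Day 56 and runs from Day 43 to Day 70), and Week 24 is open-ended from Day 155. For the on-treatment visits, "only on-drug assessments or assessments performed within 15 days post last dose are to be analyzed within those windows". Repeat, unscheduled and early termination laboratory results are not exempted.

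The protocol produces such results by design. Under Protocol 7.5.3, after a significant shift in a laboratory parameter of interest, "subjects will then be scheduled for an interim visit within 2 weeks to repeat the laboratory measurements". In Protocol 5.4, three ALT/AST criteria apply "on repeat examination (if assumed increase is related to study drug") and the creatinine criterion applies "on repeat exam (if assumed increase is related to study drug"). Laboratory samples are also taken at the early termination visit (7.2.4) and may be taken at unscheduled visits (7.2.6).

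For reporting, SAP 12.9.2 says: "Subjects with values outside the normal range will be flagged and summarized using shift tables". The same section promises complete listings, and a listing and table of subjects with markedly abnormal values. SAP Section 16 outlines chemistry and hematology summaries by visit, shifts by visit, and lymphocyte counts by Week 24 response. The shift shell contains only blocks from baseline to a named week.

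**The concern.** A closest-to-target rule suits by-visit means, because it gives each subject one comparable value per time point. It suits a shift table less well when that table is the main tabulated account of laboratory abnormality, because off-schedule draws are often prompted by a symptom or a suspicious result, and they usually lie further from the target day than the routine draw.

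Protocol 8.8 says the safety assessment rests mainly on adverse event frequency and on how many laboratory values fall outside predetermined ranges. Protocol 5.4 associates the drug class with lymphocyte, hepatic and renal effects. If a value first goes out of range at an unscheduled draw or an early termination visit, and a normal scheduled draw sits closer to target in the same window, the laboratory tables count that subject as normal for that visit. When drug is then stopped, no later on-treatment visit corrects the entry.

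**Working it through.** **Reproducing the SAP's own example.** SAP 11.4 takes a subject with last dose on Day 84 and early termination on Day 100. The gap is 100 − 84 = 16 days, more than 15, so the visit becomes Visit 9 although Day 100 lies in the Day 99 to 126 window. This matches the SAP.

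**Inputs.**
- Scheduled draw: target day plus j, with j from −3 to +3 (Protocol Table 1-1).
- Repeat: k days after that draw, with k from 1 to 14 (Protocol 7.5.3).
- Window end, Weeks 4 to 20: target + 14 (SAP 11.4).
- Choice within a window: smallest distance from target, the later visit if tied (SAP 11.4).

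That gives 7 × 14 = 98 combinations per window.

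**When the repeat is kept.** It must lie in the same window with |j + k| ≤ |j|.
- j = −3: k ≤ 6, 6 combinations.
- j = −2: k ≤ 4, 4 combinations.
- j = −1: k ≤ 2, 2 combinations.
- j = 0 or later: none.

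Total 6 + 4 + 2 = 12 of 98 (12.2%). In all 12 the scheduled value, which triggered the repeat, is the one dropped.

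**When the repeat falls in the next window.** This needs j + k > 14.
- j = 1: k = 14, 1 combination.
- j = 2: k = 13 or 14, 2 combinations.
- j = 3: k = 12 to 14, 3 combinations.

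Total 6 of 98 (6.1%). The largest j + k is 17, so such a repeat is at least 28 − 17 = 11 days from the next target. It loses to any scheduled visit within ±3 days and is used only if that visit is missing.

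**When the repeat loses in its own window.** 98 − 12 − 6 = 80 of 98 (81.6%). Week 24 has no following window, so 98 − 12 = 86 of 98 lose and 12 win.

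**Dependence on timing.** The 12% weights all day combinations equally. If every scheduled draw is on or after target, no repeat is kept (0%). If every draw is 3 days early, 6 of 14 are kept (43%). A repeat 7 or more days later never wins in its own window: of 7 × 8 = 56 such combinations, 50 lose there and 6 move to the next window.

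**A case the tables would miss.** Suppose the Week 8 draw on Day 56 is normal, an unscheduled draw on Day 65 shows the first low lymphocyte count, drug is stopped that day, and early termination is on Day 68. All three draws lie in Day 43 to 70, and Day 68 is 3 days after last dose. Distances from target are 0, 9 and 12 days, so only Day 56 is analysed. The Week 8 shift entry is normal, and no later on-treatment draw exists.

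**The case against.** The strongest reply is that little is lost. SAP 12.9.2 keeps every result in complete listings, and Section 16 adds a listing of out-of-range values (16.2.8.3). Clinically relevant laboratory changes are collected as adverse events (Protocol 7.5.1.1), events leading to drug discontinuation are summarised, and Table 14.1.1 counts discontinuation by reason. All of this stands. A reader might infer that an off-schedule abnormality appears in no table at all; the documents do not support that.

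A reader might also infer that repeats disappear from every laboratory table. That goes too far, because the markedly abnormal table is promised per subject and is not tied to one value per window. However, it cannot be relied on as it stands: laboratory thresholds are not given (vital signs have theirs in SAP 12.9.3), the values it draws on are not stated, and it has no Section 16 entry or shell.

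Nor do all hepatic and renal stopping criteria rest on the two-week repeat. The ALT/AST criterion linked to symptoms needs no repeat, and proteinuria is judged on samples 4 weeks apart. In any case the windowing rule governs analysis, not decisions at the site.

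Finally, the share of repeats not kept is not a measure of harm. The shift tables use three categories. When the repeat loses to a scheduled value that was already high or low, the subject is still counted as such. This stands, and it narrows the concern to the two situations named in the verdict.

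Protocol 8.7.3 assigns early termination data to the nearest visit without data, which could rescue some of them. But it sits under the efficacy analyses, SAP 11.4 assigns by actual study day, and Protocol 8.10 gives the SAP precedence.

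**Conclusion.** The concern holds for the outlined by-visit and shift laboratory tables. Most off-schedule values are left out of them: under equal weighting of days, scheduled visits within ±3 days and repeats at 1 to 14 days, 12% of repeats are kept per window, within a range of 0% to 43% by visit timing. A further 6% enter the next window only if its scheduled visit is missing.

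The consequence is confined to two groups: abnormalities first seen off-schedule, and original abnormal values displaced by a repeat closer to target. The documents give no basis for estimating how many subjects fall in either group. Co-primary testing, stopping decisions and the data collected are not affected. The gap is that no outlined laboratory table answers the question Protocol 8.8 puts at the centre of the safety assessment, and the promised table that might answer it is undefined. The change is worth making because it is cheap and alters what the safety tables can show.

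**What to change.** Keep the closest-to-target value for by-visit means. Then make two changes.

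1. In SAP 12.9.2 and Tables 14.3.2.4.1 and 14.3.2.4.2, add a row for the shift from baseline to the worst on-treatment value, in each direction. Use all scheduled, repeat, unscheduled and early termination results up to 15 days after last dose. The denominator is treated subjects with a baseline and at least one post-baseline value.
2. State that the markedly abnormal table uses the same all-values data, pre-specify its laboratory thresholds, and give it a Section 16 entry and shell. This is needed as well as the first change, because a low/normal/high row cannot show how far a value has worsened once it is out of range.

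The cost is SAP wording, one extra row per parameter in each direction, one shell and minor programming. No new data are needed.
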